ORI IRB# 00000278

Protocol Version 10.26.2021

Official Title: Evaluation of Phase I Fathering In Recovery Prototype

Principal Investigators: [name].

Influents Innovations

Award No. R43DA052949-01

Protocol Version Date: 10.26.2021

[figure not shown]
Study Protocol

Thirty fathers were enrolled in the Fathering In Recovery (FIR) Phase I pilot study. Fathers were recruited through residential and outpatient drug and alcohol treatment centers located across the nation. The majority were recruited from Hazelden drug and alcohol treatment centers (83%) and CODA opioid treatment centers (7%). Drug treatment staff identified individuals who they believed met eligibility criteria and were currently or had recently participated in either residential or outpatient treatment. Those individuals were provided with brief information describing the study and provided with a website address that took them to a Qualtrics screener to assess eligibility. If individuals were eligible, they were asked to provide their contact information so that research staff could follow up to provide additional information regarding the study and a consent document to enroll in the study.

Fathers were invited to complete the 4-session FIR program over 4 weeks. Fathers completed outcome questionnaires approximately 1 week prior to starting the program and approximately 1 week after completing the program. Fathers also evaluated acceptability and usability. Twenty-eight fathers completed post-intervention assessments (93% retention).

Statistical Analysis Plan

To address promise of efficacy, the primary approach will be standard normal paired sample t-tests for evaluation of pre-post improvements in the benchmark outcomes. Although this is not a randomized trial and we therefore cannot demonstrate program efficacy, a critical component of the feasibility analysis will be observed pre-post improvements in parenting knowledge, parenting efficacy, parenting skill, and pre-post reductions in substance use. We will test the hypothesis $H_1: \mu_{\text{POST}} > \mu_{\text{PRE}}$ for knowledge, efficacy, and parenting skill, and $\mu_{\text{POST}} < \mu_{\text{PRE}}$ for substance use. The paired *t*-test assumes that the paired differences individual i ($\mu_{\text{POST}} - \mu_{\text{PRE}}$) are a simple random sample from a population of normally-distributed difference values that all have the same mean and variance. This assumption implies that the data are continuous, and their distribution is symmetric. The paired sample *t* is the same formula shown above with the standard deviation given as the paired differences:

$$s = \sqrt{\frac{\sum_{i=1}^n (X_i - \bar{X})^2}{n - 1}}$$

The primary outcomes, parenting efficacy and parenting skill are measured on a Gaussian normal, the test $\mu_{\text{POST}} > \mu_{\text{PRE}}$ is powered .802 to detect a pre-post effect size of .46 standard deviations, a medium effect; likewise, for substance use also on a continuous scale on the PhenX, the test $\mu_{\text{POST}} < \mu_{\text{PRE}}$ is powered .80 to detect an effect size of .46. For all discrete outcomes such as the Phenx psychopathology, a sample size of 30 is powered .809 to detect pre-post change of .22 in proportions of the sample above item thresholds. For example, items are measured on a scale of 0 to 4, with 1 “slight” the threshold for suicidality, psychosis, and

substance use, and 2 “mild” the threshold for depression, anxiety, or sleep disorder, etc. For Poisson frequencies of substance use, the study is powered .802 to detect a .58 mean reduction in the pre-post rate of use, and effect size of .46.

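### Does the plan need a stated rule for the 2 of 30 fathers who have no post-intervention assessment?

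*Combined protocol and SAP*

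**What the plan says.** The Study Protocol section gives the enrolment, "Thirty fathers were enrolled in the Fathering In Recovery (FIR) Phase I pilot study", and the follow-up, "Twenty-eight fathers completed post-intervention assessments (93% retention".

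The Statistical Analysis Plan section makes paired t-tests the main analysis: "the primary approach will be standard normal paired sample t-tests for evaluation of pre-post improvements in the benchmark outcomes". It defines the standard deviation in that test over the individual paired differences. It says outright that a non-randomised study cannot show efficacy, and it treats the observed pre-post changes as a key part of judging feasibility. Parenting efficacy and parenting skill are named as the primary outcomes. For these the test "is powered .802 to detect a pre-post effect size of .46 standard deviations, a medium effect".

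Three further power statements follow:
- Continuous substance use: .80 power at the same .46 effect.
- Discrete outcomes: "a sample size of 30 is powered .809 to detect pre-post change of .22 in proportions of the sample above item thresholds".
- Substance-use frequencies treated as Poisson: "the study is powered .802 to detect a .58 mean reduction in the pre-post rate of use, and effect size of .46".

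Neither section states an analysis population, a missing-data rule, a sensitivity analysis or a significance level. The alternatives are directional.

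**The concern.** A paired test needs both measurements, so at most 28 of the 30 fathers can enter it, yet the plan neither says so nor says what is done about the other two. The documents give no reason for the two losses.

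In a sample recruited through drug and alcohol treatment, loss linked to relapse or disengagement is a natural worry. Were that the cause, the 28 completers would show more reduction in substance use than all 30 fathers did. No direction can be argued for the parenting outcomes.

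What would be at stake is how firm the pilot signal is. The 28-pair result alone does not tell a reader how badly the two unseen fathers would have to fare before a nominally significant reduction stopped being so. The power figures also appear to assume 30 complete pairs.

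**Working it through.** **Inputs.** From the documents: 30 enrolled, 28 with a post-test, effect .46 SD, power .802, and a .58 mean reduction in rate of use paired with an effect of .46. Assumption: one-sided α = .05, since no level is stated; two-sided .05 is shown as the range.

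**1. The plan's own power figure.** Paired t-test, df = n − 1, noncentrality d√n.
- n = 30, one-sided: .46 × √30 = 2.52. Noncentral t gives .793. The normal approximation gives Φ(2.52 − 1.645) = .809. The stated .802 lies between them.
- n = 30, two-sided: .683 (t) or .712 (normal). These do not reproduce it, which supports the one-sided reading.

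**2. Cost of losing two pairs.**
- n = 28, one-sided: .767 (t) or .785 (normal).
- Effect detectable at .80 power: .465 SD for 30 pairs, .482 SD for 28.

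**3. How bad would the two missing fathers have to be?** Take 28 differences with mean .46 and SD 1 (positive means improvement). Add two fathers with change x each, and recompute the mean M and SD over all 30:

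M = (28 × .46 + 2x)/30; SS = 27 × 1² + 28(.46 − M)² + 2(x − M)²; t = M / √(SS/29/30), on 29 df.

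| Case | M | t | one-sided p |
|---|---|---|---|
| 28 completers only (27 df) | .46 | 2.43 | .011 |
| both unchanged (x = 0) | .429 | 2.42 | .011 |
| both x = −1 SD | .363 | 1.92 | .032 |
| both x = −2 SD | .296 | 1.41 | .084 |

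The p-value reaches .05 at x = −1.43 SD for both fathers, or −2.54 SD if only one worsened and the other did not change. With two-sided .05 the joint value is −.76 SD. The same SD figures apply to the parenting outcomes, which share the .46 effect.

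**4. On the rate-of-use scale.** Implied SD of change = .58/.46 = 1.26.
- Tipping value: 1.428 × 1.261 = 1.80 more units of use in each father (.96 if two-sided). That is 1.80 + .58 = 2.38 units, or 2.38/1.261 = 1.89 SD, worse than the completers' mean.
- At +2 units each: mean reduction (28 × .58 − 4)/30 = .41, p = .058.
- At +3 units each: (28 × .58 − 6)/30 = .34, p = .114.
- Mean reduction falls to zero only at 28 × .58/2 = 8.12 units each, or 8.12/1.261 = 6.4 SD.

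**5. Threshold outcomes.** Suppose 6 of 28 improve and none worsen (6/28 = .21, near the plan's .22), and count each missing father as above threshold. A father already above threshold at baseline adds no discordant pair; one who was below adds a worsening.

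| Improved v worsened | exact one-sided McNemar p | normal approximation p |
|---|---|---|
| 6 v 0 | .016 | .007 |
| 6 v 1 | .063 | .029 |
| 6 v 2 | .145 | .079 |

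The verdict on 6 v 1 depends on which test is used, and the plan names none. With 7 v 1, even the exact test gives .035.

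**The case for a change.** The strongest case for acting is that the cost is trivial: a sentence giving the number of pairs, the two fathers' baseline values, and a sensitivity line labelled post hoc. The fragility is also not imaginary. A completer effect of .40 SD would tip at −.87 SD in each missing father. A borderline effect of .32 SD (p = .050) would move to .11 if both worsened by 1 SD. In the threshold example, one unfavourable father is enough to lose significance under the exact test.

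The silence is real and the arithmetic is right. What does not stand is the inference that the plan is deficient:
- A borderline p-value is visibly borderline, and no missing-data rule is needed to see that.
- The tipping points rest on a criterion, p < .05, that the plan neither states nor attaches to any claim.
- The 1.8-unit figure takes an effect from the Poisson frequency statement and puts it through a t-test. It is on a scale whose unit is not given, and it describes a planned effect, not observed data.
- It also puts substance use ahead of the two outcomes the plan names as primary, for which no direction of bias can be argued.
- Relapse as the cause of the two losses is conjecture.

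**Conclusion.** No change is needed. The omission is a detail that any analyst fills the same way: the test is defined on paired differences, a father with no post-test has no difference, and the count of 28 is already disclosed. Following the plan as written gives a straightforward completer analysis at 28/30 = 93% retention.

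The effect of the two losses is small. Power at .46 SD moves from .79 to .77, and restating planning power after follow-up would affect no decision. Setting both missing fathers to no change leaves p at .011. Reversing nominal significance at the planned effect needs both of them to worsen by 1.43 SD (.76 SD if two-sided). Removing the mean reduction in rate of use needs about 8.1 units each. A tipping-point table could be offered in a report as a post hoc extra, but it would leave the primary test and every conclusion the SAP allows itself unchanged.

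These figures assume a one-sided .05 level, inferred from the directional hypotheses and the stated power. They also assume an SD of change of 1.26 on the rate-of-use scale, the planned effect rather than observed data, and a single value given to both missing fathers.

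### Does the missing significance level leave the SAP's pre-post tests and its continuous-outcome power figures undefined?

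*Combined protocol and SAP*

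**What the plan says.** The Statistical Analysis Plan section states that "the primary approach will be standard normal paired sample t-tests for evaluation of pre-post improvements in the benchmark outcomes". It then sets out directional alternatives: the post-programme mean exceeds the pre-programme mean for knowledge, efficacy and skill, and falls below it for substance use. The t statistic is formed "with the standard deviation given as the paired differences", so the effect size is read here in units of the SD of the differences.

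Four power statements follow:

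- Parenting efficacy and skill: the test "is powered .802 to detect a pre-post effect size of .46 standard deviations, a medium effect".
- Continuous substance use: the test "is powered .80 to detect an effect size of .46".
- Discrete outcomes: "a sample size of 30 is powered .809 to detect pre-post change of .22 in proportions of the sample above item thresholds".
- Poisson frequencies: "the study is powered .802 to detect a .58 mean reduction in the pre-post rate of use, and effect size of .46".

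The first two each restate the direction of the test. Only the third gives a sample size. Neither the SAP section nor the Study Protocol section gives an alpha, a p-value threshold, a confidence level, or the words one-sided or two-sided. The Study Protocol section reports 30 fathers enrolled and 28 with post-intervention assessments.

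**The concern.** The significance level is the rule by which an improvement is called significant, and it is a required input to any power figure. A directional alternative suggests a one-sided test but does not set its level: one-sided .05 and one-sided .025 both fit the wording, and the second has the same rejection threshold in the hypothesised direction as a two-sided .05 test.

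A reader who assumed two-sided .05 would find the continuous power figures about 9 to 12 points too high. That reader would also apply a stricter threshold to the results, so a modest observed change could be called significant under one convention and not under the other. The SAP calls pre-post improvement a critical component of the feasibility analysis and names several outcomes, so the ambiguity would recur.

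**Working it through.** **Inputs.** Effect size .46 SD of the paired differences (SAP, power paragraph). Sample size 30: the SAP attaches it to the discrete outcomes only, so using it for the continuous outcomes is an inference, supported by the 30 enrolled. The significance level is not given, so several values are tried.

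**Formulas.** For n pairs and standardised effect d:

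- Exact: power = P(T > t_crit), where T is noncentral t with n − 1 degrees of freedom and noncentrality d√n.
- Normal approximation: power = Φ(d√n − z_crit).

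Here d√n = .46 × √30 = .46 × 5.477 = 2.520.

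**Reproducing the stated .802 and .80.** At one-sided .05 the normal approximation is Φ(2.520 − 1.645) = Φ(.875) = .809.

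| Level, 30 pairs | Exact t | Normal approximation |
|---|---|---|
| One-sided .05 | .793 | .809 |
| One-sided .025 (two-sided .05) | .683 | .712 |
| One-sided .01 | .530 | .577 |

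One-sided .10 gives .885 by exact t. Only one-sided .05 comes within about a point of the stated values. Two-sided .10 gives the same power, but the plan mentions no two-sided test.

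**Solving backwards.** With 30 pairs and d = .46, the one-sided level that yields exactly .802 is .053 by exact t and .047 by normal approximation; these lie on either side of .05. Rounding of the effect size accounts for the remainder. The normal approximation reaches .802 at d = .4553, and exact t reaches .80 at d = .4649. Both round to .46.

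**What the other reading would change.** The observed mean change needed for significance is t_crit/√n:

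- One-sided .05: 1.6991/5.477 = .310 SD.
- Two-sided .05: 2.0452/5.477 = .373 SD.

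The probability of landing between the two thresholds is the difference between the two powers (exact t, 30 pairs):

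| True effect (SD) | Probability |
|---|---|
| 0 | .025 |
| .30 | .129 |
| .46 | .110 |
| .60 | .053 |
| .80 | .007 |

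**Achieved sample.** With the 28 fathers who completed the post-assessment, one-sided .05 gives .767 exact or .785 by normal approximation at .46 SD. This describes the sample obtained and says nothing against the planning figure.

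**The case for a change.** The strongest case for a change is that a decision rule should be written down and not deduced from power figures. At the design effect of .46 SD there is roughly a one-in-nine chance per outcome (.110) that the significance call turns on the convention used. Adding a sentence costs almost nothing, and a documented level would protect the sponsor from the charge that sidedness was chosen after the data were seen.

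The omission itself stands: no level is stated, and inferring one does not replace stating it. The rest is weaker than it looks.

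- The one-in-nine figure needs a reader to adopt two-sided .05 (or one-sided .025), which runs against the directional hypotheses and does not reproduce the stated power. It also belongs to one true effect; over the range shown it runs from .007 to .129.
- This version of the document already reports completed post-intervention assessments, so a level added to it now could not be prospective. What remains useful is disclosure of the level that was used, which belongs in the report of results.
- A general sentence saying that all the power figures assume 30 complete pairs at one level would claim more than has been checked. The discrete .809 depends on the baseline proportion and on how pairing was handled, neither of which is given, and the Poisson .802 was not reproduced. Their basis is for the sponsor to confirm.
- The SAP says that the design is not randomised and cannot demonstrate efficacy. No confirmatory claim rests on the threshold.

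**Conclusion.** The concern is correct as an observation but does not call for a change to the plan. The SAP omits the significance level, yet its directional alternatives and its continuous power figures agree with one natural reading: one-sided .05 with 30 complete pairs, giving .793 exact and .809 by normal approximation against the stated .802 and .80. An analyst following the plan on that reading applies a coherent rule, and no stated continuous power figure is shown to be wrong. The fall to .683 or .712 arises only under a two-sided .05 reading that the text does not support.

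This rests on two assumptions: that the sample size of 30 applies to the continuous outcomes, and that the level was one-sided .05, which is inferred from the arithmetic and not stated. It does not extend to the discrete and Poisson figures. As a reporting note only, the results should state the level and sidedness actually used, and that the continuous-outcome power assumed 30 complete pairs at that level.

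### Does placing substance use on three scales leave its hypothesis without a deciding test?

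*Combined protocol and SAP*

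**What the plan says.** All of the relevant text is in the Statistical Analysis Plan section of the combined document.

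- **Method.** "the primary approach will be standard normal paired sample t-tests for evaluation of pre-post improvements in the benchmark outcomes". Of this test the plan adds: "This assumption implies that the data are continuous, and their distribution is symmetric".
- **Outcomes.** The feasibility analysis looks for change in parenting knowledge, "parenting efficacy, parenting skill, and pre-post reductions in substance use". For substance use the hypothesis is that the post-programme mean is below the pre-programme mean.
- **Primary outcomes.** Parenting efficacy and parenting skill are named as primary. Substance use follows them, joined by a *likewise*.
- **Continuous version.** "likewise, for substance use also on a continuous scale on the PhenX", with power .80 at an effect size of .46. The hypothesis about the two means is written out again here.
- **Discrete version.** For discrete outcomes, with PhenX psychopathology as the named case, "a sample size of 30 is powered .809 to detect pre-post change of .22 in proportions of the sample above item thresholds". The next sentence is an example on 0-to-4 items, in which 1 (slight) is "the threshold for suicidality, psychosis, and" then "substance use, and 2 “mild” the threshold for depression, anxiety, or sleep disorder, etc".
- **Count version.** "For Poisson frequencies of substance use, the study is powered .802 to detect a .58 mean reduction in the pre-post rate of use", again with an effect size of .46.

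The section gives no alpha level, no ranking of the three versions, and no named test for the discrete or count version.

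**The concern.** One hypothesis with three power statements looks like one hypothesis with three possible answers. If the analyst could test all three and report whichever reached significance, the false-positive rate for substance use would exceed its nominal level. If the three disagreed, nothing explicit would settle the matter. The plan counts reduced substance use within a critical part of its feasibility analysis, so the claim of promise could come to rest on a scale picked after the data were seen. The Study Protocol section already reports 28 completed post-programme assessments in the past tense, so that possibility is not merely theoretical.

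**Working it through.** **Inputs from the plan.** n = 30; effect size .46 for the continuous and count versions; change of .22 for the discrete version; powers .80, .809 and .802.

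**Assumptions.** One-sided alpha of .05 (the plan gives none), and an equal correlation r of .5, .7 or .9 between the test statistics (the plan gives none).

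**Step 1: reproduce the plan's power and check the assumed alpha.** The noncentrality is .46 × √30 = 2.520.

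- One-sided, normal formula: Φ(2.520 − 1.645) = .809. Paired t (noncentral t, 29 df): .793.
- Two-sided, normal formula: Φ(2.520 − 1.960) = .712. Paired t: .683.

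The stated .80 and .802 fit one-sided .05 and do not fit two-sided .05. For the discrete version, an exact one-sample binomial test of .50 against .28 gives .806, close to .809; the .50 baseline is an assumption. None of the stated powers is in dispute.

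**Step 2: false positives if any version may count.** With k standard normal statistics of common correlation r, P(at least one significant) = 1 − P(all k below 1.645).

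| r | Three versions | Continuous and count only |
|---|---|---|
| .5 | 11.8% | 8.8% |
| .7 | 10.3% | 8.0% |
| .9 | 8.0% | 6.8% |

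**Step 3: mixed verdicts if every true effect equals its design value.** Means are set so that the powers equal the plan's figures, and P(mixed) = 1 − P(all significant) − P(none significant).

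| r | Three: all | Three: none | Three: mixed | Continuous and count only: mixed |
|---|---|---|---|---|
| .5 | .617 | .049 | 33% | 22.5% |
| .7 | .664 | .078 | 26% | 17.4% |
| .9 | .726 | .125 | 15% | 10.0% |

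**Step 4: does the plan create the situation that Steps 2 and 3 describe?** Both steps need all versions to be tested and none to take precedence. Set against the text:

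- The hypothesis concerns means. A proportion above a cut-off is not the quantity it names.
- The primary method is the paired t-test, described as implying continuous data. Of the three versions, only the PhenX scale is called continuous.
- The hypothesis is restated for substance use in one place only, the continuous PhenX statement.
- The discrete statement is about discrete outcomes in general. Substance use enters through an example listing item cut-offs, beside suicidality, psychosis, depression, anxiety and sleep.
- The count statement repeats the effect size of .46. Dividing, .58 / .46 = 1.26 is the implied standard deviation. It can be read as the same sensitivity expressed for count data.
- These are statements of power. None says that all three tests will be run or that one significant result is enough.

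Read together, the method, the hypothesis and the continuous power statement point to one variable and one test. On that reading there is a single test at 5%, and the inflation in Step 2 does not arise.

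**The case for a change.** The strongest reply is that this reading is inferred, not written. The count version is also a reduction in a mean, so wording the hypothesis in means does not exclude it. A primary approach that covers every benchmark outcome picks a method, not a variable. Giving each version its own power suggests that each might be tested. Setting the discrete version aside still leaves two candidates, with 7% to 9% false positives if either could count.

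Part of this stands: no sentence states the role of the count analysis or of the cut-off, and one line would have removed the doubt. It does not show that the plan leads to a wrong conclusion. Such a line would record the scale and test that the text already points to, not a better method. The section also refers to a formula shown above that does not appear, so it may be an excerpt from a longer text; the absence of a ranking is therefore weak evidence that none was set.

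The mixed-verdict percentages add little. Imperfectly correlated tests with about 80% power will often disagree, whatever the plan says about precedence. Those figures also need every true effect to sit at its design value at once.

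**Conclusion.** The concern does not call for a change. What is missing is an explicit statement of a hierarchy that the plan implies, and an analyst would fill it sensibly: the paired t-test on the continuous PhenX score decides, and the other versions describe. On that reading the error rate for substance use stays at the nominal 5%.

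The inflation to 7–9% (two versions) or 8–12% (three) applies only if an analyst ignored that reading and let any significant version count. It also rests on one-sided .05, which is inferred from the plan's power figures, and on correlations of .9 to .5, which are assumed.

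Even then the consequence is small. The plan says that the design cannot demonstrate efficacy, parenting efficacy and parenting skill are the named primary outcomes and are untouched, and the sample is 30 fathers without a control group.

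### Should the PhenX depression, anxiety and sleep items be tested on their 0–4 scores rather than as a proportion above threshold?

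*Combined protocol and SAP*

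**What the plan says.** The Statistical Analysis Plan names one test, the paired t-test, and ties it to the benchmark outcomes: parenting knowledge, efficacy, skill and substance use. It says of the test's assumption: "This assumption implies that the data are continuous, and their distribution is symmetric".

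Discrete outcomes, with PhenX psychopathology as the example, get a power statement only: "a sample size of 30 is powered .809 to detect" a difference defined as "to detect pre-post change of .22 in proportions of the sample above item thresholds". The plan explains that "items are measured on a scale of 0 to 4". It then sets two cuts: 1 is "the threshold for suicidality, psychosis, and" substance use, and 2 is "the threshold for depression, anxiety, or sleep disorder, etc".

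For these items it states no test, alpha, baseline prevalence or pre-post correlation. It does not say whether a score equal to the threshold counts as above it. Substance use is also planned as continuous ("for substance use also on a continuous scale on the PhenX") and as a Poisson count, so the question concerns the psychopathology items cut at 2. The Study Protocol section reports that 28 of the 30 enrolled fathers completed the post-intervention assessment.

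**The concern.** Reducing a 0–4 score to a yes/no at 2 loses information. If a score of 2 counts as above, a father who goes from 4 to 2, or from 1 to 0, is recorded as unchanged. With 28 pairs that loss could matter, and the scores are collected anyway.

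Nor does the plan offer an obvious alternative. Its only named test is described as needing continuous, symmetric data, which a single five-level item does not supply. On that reading neither the proportions nor the scores have a suitable named test, and a real improvement in depression, anxiety or sleep spread over the scale would be missed more often than necessary. The natural remedy would be a Wilcoxon signed-rank test on the score differences, with the proportions reported descriptively.

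**Working it through.** **Inputs.** From the documents: n = 30, power .809, change of .22, scale 0–4, cut at 2, 28 completers. Assumed because the documents are silent: alpha .05, baseline distribution, pre-post correlation and shape of change.

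**1. The plan's own figure.** At one-sided .05 with n = 30, take an exact binomial test of .50 against .50 + .22 = .72 that rejects at 20 or more.
- Size: P(X ≥ 20 | .50) = .0494.
- Power: P(X ≥ 20 | .72) = .806.

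Exact McNemar with nobody worsening needs at least 5 falls (.5⁵ = .031; .5⁴ = .0625 is too large). P(X ≥ 5) for X ~ Bin(30, .22) is .821. Both are within two points of .809. Two-sided .05 gives .681 and .674, which do not fit. The stated power is therefore consistent with a one-sided test of a proportion.

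**2. Scores against proportion, same sidedness.** 28 pairs, latent normal scores cut into five levels, 50% at or above 2 at baseline, two-sided .05. Each cell gives power at correlation .4 / .6.

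| Assumed change | Signed-rank on 0–4 | McNemar at cut 2 |
|---|---|---|
| All shift .5 SD | .54 / .70 | .35 / .42 |
| Half shift 1 SD | .42 / .53 | .28 / .32 |
| 35% fall to 0 | .45 / .52 | .28 / .31 |
| Half capped at 1 | .35 / .41 | .52 / .57 |

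Over baselines with 50, 31, 21 and 10% at or above 2, McNemar's relative loss in the first three rows is 36–54%, 34–45% and 33–42% (one-sided .05: 24–40%, 23–36% and 27–36%). In the fourth row McNemar has 38–86% more power (one-sided 31–71%). If only scores strictly above 2 count, the uniform-shift loss is larger, 53–90% two-sided.

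**3. What drives the reversal.** The fourth row draws pre and post scores at correlation .4 or .6, so scores also move at random around the cut. Suppose instead that every change is a single step across the cut. All m non-zero differences then have size 1 and share one rank. The signed-rank statistic is proportional to the number of falls, which is Bin(m, ½) under the null, and that is exact McNemar. Exact one-sided tests at n = 30, with the net drop fixed at the plan's .22, show the range:

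- Change spread over the scale, correlation .3/.5/.7: signed-rank about .74/.83/.94, McNemar .50/.53/.62.
- One-step crossings only, nobody worsening: .815 for both.
- The same, with 10/25/50% of the other fathers moving at random on their own side of the cut: signed-rank .67/.54/.41, McNemar .81 to .83.
- Crossings of one to four steps, nobody worsening: signed-rank .75 to .84, McNemar .81 to .83.

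**4. The remedy against the test implied by .809.** A two-sided signed-rank test compared with one-sided McNemar (28 pairs, 50% prevalence, correlation .4 / .6):

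| Assumed change | Signed-rank, two-sided | McNemar, one-sided |
|---|---|---|
| All shift .5 SD | .55 / .70 | .53 / .59 |
| Half shift 1 SD | .43 / .53 | .43 / .48 |
| 35% fall to 0 | .46 / .52 | .44 / .47 |

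The largest gain over 24 settings (three models, four baselines, two correlations) is about .11: .70 − .59 in the first row. In 12 of the 24 signed-rank is equal or lower, some of these within simulation error.

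**5. Whether the t-test is unusable on the scores.** In the cut-2 simulations its one-sided size is .049–.051 and its power is within .017 of signed-rank. An analyst who wants a score analysis can use the test that the plan already names.

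**The case for a change.** The best argument for a change is that the power advantage is real and robust within its conditions. When change is spread over the scale, the scores win in every setting tried: both readings of the cut, 28 or 30 pairs, one- or two-sided. A one-sided signed-rank test would keep that advantage over one-sided McNemar, so the result in step 4 counts against a two-sided remedy and not against score analysis as such. Leaving the test and the cut unspecified also lets both be chosen after the data are seen.

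The conditional power claim stands. It does not settle the choice, because the condition is a guess about how these fathers' symptoms move, and because a proportion over a threshold and a location shift on a scale are different targets. The plan sets thresholds domain by domain, 1 for some and 2 for others, which fits an intention to count fathers over a threshold. If that is the target, the proportion is the right quantity whatever its relative power.

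The point about choice after the data also stands, but it concerns missing detail. A paired comparison of proportions has a standard test, and a cut described as a threshold is readily taken to include its own value. Follow-up is already reported as complete, so a new primary test for these items might itself have to be declared post hoc.

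**Conclusion.** No change to the plan is needed. Comparing proportions gives up power if improvement is spread over the scale (relative loss of roughly a third to a half, two-sided, under the assumed models). It matches the score test if all change is one step across the cut. It does better if small crossings sit among background fluctuation. Every one of these sizes rests on assumed distributions, correlations and change shapes, and only two of the four baselines examined (50% and 31%) allow a .22 drop at all under the change models used.

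That is a fair trade-off between two defensible targets, and the plan describes one of them. The unnamed test, the unstated alpha and the undefined edge of the threshold are gaps that a competent analyst fills with a paired test of proportions, adding a score analysis as an exploratory supplement if wanted. Little depends on them: psychopathology is neither a primary nor a listed benchmark outcome, and the plan itself says that an uncontrolled pre-post study cannot demonstrate efficacy.
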